- Change from baseline in best-corrected visual acuity (BCVA) at 1, 2, 3, 6, 9, and 12 months
- Change from baseline in visual field assessed by Octopus 900 perimeter at 3, 6, and 12 months

Exploratory Endpoints:

Study Design: This is a Phase 1/2/3, first-in-human, multi-center, dose-escalation interventional study of AAV8-RPGR in male subjects with genetically confirmed XLRP. Part I is a dose-escalation study; Part II is a dose-escalation study, with 2 doses (2.5×10^{11}) vector genomes (vg) [high dose], 5×10^{10} vg [low dose]) selected from Part I based on a benefit/risk assessment, and a third untreated group to allow for a controlled comparison of efficacy and safety.

Part I consists of 11 visits over a 24-month evaluation period. Part II consists of 10 visits over a 12-month evaluation period. At the Screening / Baseline Visit, each subject will be assessed for eligibility of both eyes. Only 1 eye will be randomized (the "study eye"), and the other eye will be designated as the "fellow eye". Selection of the "study eye" will be made on clinical grounds prior to randomization and will generally be the worse eye affected.

At the Injection Day Visit (Visit 2, Day 0), subjects will undergo vitrectomy and iatrogenic retinal detachment as part of a sub-retinal injection procedure for administration of AAV8-RPGR in their study eye. Subjects in the untreated control group will receive study-visit telephone calls to monitor AEs/SAEs and review concomitant medications on Visit 2 (Day 0) and on Visits 3 and 4 (post-operative Days 1 and 7).

To minimise inflammation resulting from surgery and/or vector/transgene, in Part I, all subjects will be given a 21-day course of oral corticosteroid (e.g., prednisolone/prednisone) that will start 2 days before the planned date of surgery.

In Part II, all adult subjects will be given a 9-week course of oral corticosteroid starting 3 days before surgery: 21 days at 60 mg, followed by 6 weeks of tapering doses. The dose regimen is adjusted for pediatric subjects treated in Part II (see Section 8.8). Subjects may also be treated at the time of surgery with up to 1 mL of triamcinolone (40 mg/mL), administered via a deep subTenon approach.

Part I: Dose-Escalation Study

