At the Injection Day Visit (Visit 2, Day 0), subjects will undergo vitrectomy and iatrogenic retinal detachment as part of a sub-retinal injection procedure for administration of AAV8-RPGR in their study eye. To minimise inflammation resulting from surgery and/or vector/transgene, in Part I, all subjects will be given a 21-day course of oral corticosteroid (e.g., prednisolone/prednisone) that will start 2 days before the planned date of surgery (see Section 8.8 for details). In Part II, all subjects may be treated at the time of surgery with up to 1 mL of triamcinolone (40 mg/mL), administered via a deep sub-Tenon approach. Subjects will also be given a 9-week course of oral corticosteroid starting 3 days before surgery: 21 days at 60 mg, followed by 6 weeks of tapering doses. The dose regimen is adjusted for pediatric subjects treated in Part II (see Section 8.8).

Subjects in the untreated control group will receive study-visit telephone calls to monitor AEs/SAEs and review concomitant medications on Visit 2 (Day 0) and on Visits 3 and 4 (post-operative Days 1 and 7).

Subjects will be assessed for safety and efficacy throughout the study as indicated in the Schedule of Study Procedures (see Section 16.1). The safety evaluation will be based on the

occurrence of adverse event (AE) reporting (including DLTs); full ophthalmic examination (including indirect ophthalmoscopy, slit-lamp examination, intraocular pressure [IOP], anterior chamber and vitreous inflammation grading and lens opacities classification system III [LOCS III] cataract grading); fundus photography; vital signs; and laboratory assessments (including laboratory safety parameters, viral shedding and immunogenicity).

The efficacy evaluation will be based on microperimetry, BCVA, SD-OCT, fundus autofluorescence, visual fields (Octopus 900 specified in Part II only), contrast sensitivity, low luminance visual acuity (LLVA),

Any safety information collected as a result of the efficacy assessments (e.g., BCVA) will also be used in the overall safety evaluation, as applicable.

Subjects who develop cataracts may undergo cataract surgery if deemed clinically necessary; if surgery is performed, it should be carried out at least 4 weeks before their final visit.

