Application of AAV8-RPGR to the under-surface of the retina requires retinal detachment following vitrectomy. As such, sub-retinal injection of AAV8-RPGR carries the risks associated with vitrectomy and retinal detachment, which include intra-operative and post-operative complications: infection (most notably infectious endophthalmitis); low and elevated IOP; choroidal detachment; macular oedema; vitreous haemorrhage; visual impairment; metamorphopsia; and photopsia (Park, Marcus et al. 1995, Thompson, Sjaarda et al. 1996, Banker, Freeman et al. 1997, Cheng, Azen et al. 2001, Anderson, Fineman et al. 2006, Stein, Zacks et al. 2009, Recchia, Scott et al. 2010). Post-operative intraocular inflammation caused by vitrectomy is often associated with transient visual impairment. A long-term complication of vitrectomy is cataract formation, which may require an additional surgical procedure (cataract extraction) (Park, Marcus et al. 1995, Cheng, Azen et al. 2001, Recchia, Scott et al. 2010). To minimise inflammation resulting from potential immune responses to vector, subjects receiving AAV8-RPGR will be given a course of oral corticosteroid (see Section 8.8 for details).

Once Part I dose-escalation has been completed, and the safety and tolerability of AAV8-RPGR is demonstrated in adults, subjects ≥10 years of age will be enrolled in Part II of the study. The 10-years of age cut-off safeguards that participating pediatric subjects will be able to comply, adequately perform study assessments, and have sufficiently advanced disease that is encroaching on the macula (i.e., the AAV8-RPGR treatment administration area).

In Part II, subjects will be randomized to a high-dose $(2.5 \times 10^{11} \text{ vg})$, a low-dose $(5 \times 10^{10} \text{ vg})$, and an untreated group. This allows for comparisons in a randomized and controlled fashion, as recommended by regulators for best practices in ophthalmic gene therapy studies (FDA 2018). The sponsor, investigator and the subject will be unmasked to the study procedure and treatment (i.e. vitrectomy and sub-retinal injection). However, within the treated groups, the sponsor, investigator, and subject will be masked (i.e. double-masked) to the assigned dose. To further minimise potential bias of the treated and non-treated eye

AAV8-RPGR Version 11.0 Protocol: NSR-RPGR-01 1 Oct 2020

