8.8. Concomitant Therapy

Subjects cannot have participated in another research study involving an investigational product in the past 12 weeks or received a gene/cell-based therapy at any time previously (including, but not limited to, IRIS implantation, ciliary neurotrophic factor therapy, nerve growth factor therapy).

Throughout the study, subjects may be prescribed any concomitant medications, procedures and/ or treatments deemed necessary for the subjects' ongoing medical care. Details of medications, treatments and procedures will be collected at the Screening/Baseline Visit and updated at every study visit (including the ET Visit, if applicable). Concomitant medications (including prednisone/prednisolone), treatments and procedures taken/undergone during the study are to be recorded in the subject's medical records and eCRF; an exception to this is any medication used in the course of conducting a study assessment (e.g., topical anesthesia, dilating eye drops).

To minimise inflammation resulting from surgery and potential or unexpected immune responses to vector/transgene, all subjects will be treated with a course of corticosteroid therapy.

In Part I, all subjects will be prescribed a 21-day course of oral prednisone/prednisolone following closely the 17-day protocol established in the voretigene neparvovec-rzyl AAV gene therapy clinical trial for treatment of patients with confirmed biallelic RPE65 mutation-associated retinal dystrophy (Maguire, Simonelli et al. 2008), allowing an extra 4 days for tapering the dose at the end of the course, i.e., 1 mg/kg/day prednisone/prednisolone for a total of 10 days (beginning 2 days before the vector injection, on the day of injection, and then for 7 days); followed by 0.5 mg/kg/day for 7 days; 0.25 mg/kg/day for 2 days; and 0.125 mg/kg/day for 2 days (21 days in total).

In Part II, all subjects will be prescribed a course of oral corticosteroids. In addition, at the time of surgery, subjects (adult and pediatric) may be treated with up to 1 mL of triamcinolone, 40 mg/mL solution, which must be administered via a deep sub-Tenon approach.

For adults, 60 mg of oral prednisone/prednisolone will be prescribed for the initial 21 days (starting 3 days prior to surgery), followed by a weekly taper as follows, for a total of 9 weeks of treatment:

```
Day -3 through day 17 (21 days): 60 mg by mouth once daily
```

Day 18 through day 24 (7 days): 50 mg by mouth once daily

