If subject was not previously in XOLARIS study, BCVA assessments at baseline must be performed in triplicate.

For all subjects who require triplicate BCVA testing, to facilitate the additional BCVA measures, this visit should be conducted over 2 days, with BCVA measured twice on Day 1 and once on Day 2 (prior to pupil dilation). All 3 BCVA values must be recorded in the eCRF. The highest score will be used to define subject eligibility.

- 3. Assessments at screening collected in triplicate. To facilitate triplicate testing, the visit should be conducted over 2 days. Visual field and microperimetry outputs will be sent to a CRC for review. Data will be generated and collated within the CRC and exported to the Sponsor or designee. For microperimetry, the last assessment performed during screening will be used for assessing eligibility and will be defined as the baseline assessment.
- 4. Octopus 900 perimeter is specified for visual field assessments only in Part II.

Subjects who meet all the inclusion criteria and none of the exclusion criteria will have a study eye assigned and be enrolled into the study. In Part II, subjects will be informed of the randomisation outcome (i.e., AAV8-RPGR treatment or the Control group) and instructed to not reveal their treatment group assignment to the masked assessors during the study. Subjects randomised to the AAV8-RPGR treatment groups (along with the Investigators and sponsor) will remain masked to the assigned dose.

See Section 8.5 for details on randomisation and assignment of subject numbers.

The next study visit (Visit 2) is to be scheduled within 12 weeks of the Screening/Baseline Visit. Subjects will be given a course of oral prednisone/prednisolone and instructed to start taking the drug 2 days (Part I) or 3 days (Part II) before their next study visit (Visit 2). Where applicable, subjects will also be instructed to use barrier contraception or abstain from sexual intercourse for a period of 3 months from the time they are treated.

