- b. Although the visit will still be considered out-of-window, if a subject in Part II is unable to attend the 12-month visit during the protocol-defined window, they should return to the site to complete this visit as soon as it is possible for them to do so. Delays will be identified as PDs on a case-by-case basis by the Sponsor based on information provided by the site; this will include but is not limited to scenarios such as site closure, travel bans, medical travel prohibitions, patient illness, etc.
- c. Visits 10 and 11 are for Part I subjects only

- d. Although the visit will still be considered out-of-window, if a subject in Part I is unable to attend the 24-month visit during the protocol-defined window, they should return to the site to complete this visit as soon as it is possible for them to do so. Delays will be identified as PDs on a case-by-case basis by the Sponsor based on information provided by the site; this will include but is not limited to scenarios such as site closure, travel bans, medical travel prohibitions, patient illness, etc.
- e. An early termination (ET) visit is to be performed if a subject discontinues at any time.
- f. If clinically indicated, subjects may need to return to the site for an unscheduled visit. At a minimum, the following assessments will be performed: full ophthalmic examination, BCVA, SD-OCT, microperimetry (if clinically feasible), fundus autofluorescence, AE/SAE monitoring, and concomitant medication, treatments, and procedures review
- g. Visits 2, 3, and 4 will be a telephone call only for subjects randomised to the control, untreated group. AE/SAE monitoring and concomitant medication, treatments, and procedures review will be assessed during the call.
- h. Includes hematology and clinical chemistry
- i. To be conducted only if unavailable at Visit 1
- j. Includes indirect ophthalmoscopy, slit lamp examination, IOP, anterior chamber and vitreous inflammation grading and LOCS III cataract grading
- k. Study eye only
- 1. Part I subjects will take 1 mg/kg/day prednisone/prednisolone for a total of 10 days (beginning 2 days before the vector injection, on the day of injection, and then for 7 days); followed by 0.5 mg/kg/day for 7 days; 0.25 mg/kg/day for 2 days; and 0.125 mg/kg/day for 2 days (21 days in total). Part II subjects in treated groups will be given a 9-week course of oral prednisone/prednisolone and instructed to start taking the drug 3 days before Visit 2. See Section 8.8.

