- m. Part I subjects perform BCVA assessments in triplicate at baseline, Month 12, Month 24, and at the Early Termination visit, when applicable. For Part II subjects only: if the BCVA value at Visit 1 (Screening/Baseline) is ≥ ± 10 letter gain or loss in the study eye compared to the previous XOLARIS study visit (if applicable), then BCVA must be repeated an additional 2 times, resulting in a total of 3 BCVA measures at Visit 1.

 In Part II subjects, if the BCVA value at Visit 1 (Screening/Baseline) is < ± 10 letter difference in the study eye compared to the previous XOLARIS study visit, then BCVA will be collected once and will not be repeated. If subject was not previously in XOLARIS study, BCVA assessments at baseline must be triplicate.
 - For all subjects who require triplicate BCVA testing, to facilitate the additional BCVA measures, this visit should be conducted over 2 days, with BCVA measured twice on Day 1 and once on Day 2 (prior to pupil dilation). All 3 BCVA values must be recorded in the eCRF. At screening, the highest score will be used to define subject eligibility.
- n. Subjects perform triplicate microperimetry only at baseline. The final microperimetry assessment will be used to determine eligibility. Microperimetry should be conducted at unscheduled visits, if clinically feasible. Microperimetry outputs will be sent to a CRC for review. Data will be generated and collated within the CRC and exported to the Sponsor or designee for inclusion in the study database.
- o. Triplicate at baseline. Octopus 900 perimeter is specified for visual field assessments only in Part II. Visual field outputs will be sent to a CRC for review. Data will be generated and collated within the CRC and exported to the Sponsor or designee for inclusion in the study database.
- q. Blood, tears (both eyes), saliva, and urine samples will be collected for the viral shedding assay.
- r. Immunogenicity sampling at the ET Visit is to be conducted only if visit occurs prior to Month 12 visit.
- s. AEs/SAEs will be collected from the time the subject provides written informed consent/assent through to the last study visit (or ET Visit if applicable).
- t. Corticosteroid review is applicable only for treated subjects.
- u. Part II only.

Biogen MA Inc. [name]

Biogen Idec Research Limited [name]

AMENDMENT SUMMARY

Biogen Protocol 274RP101 (NSR-RPGR-01)

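### Protocol Sections 8.8 and 9.1 do not limit the Part II oral steroid course to treated subjects, while Section 6.3 and the Table 3 footnote do

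*Protocol*

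**What the plan says.** Four places in the current protocol (Version 11) describe the course without limiting it to the treated arms:

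- Section 8.8, first for the study as a whole: "all subjects will be treated with a course of corticosteroid therapy". Then for Part II: "In Part II, all subjects will be prescribed a course of oral corticosteroids".
- Section 9.1, at the screening visit where the drug is handed out: "Subjects will be given a course of oral prednisone/prednisolone and instructed to start taking the drug". The start is set at 3 days before Visit 2 for Part II.
- Synopsis: "In Part II, all adult subjects will be given a 9-week course of oral corticosteroid starting 3 days before surgery". Children are covered by a cross-reference to Section 8.8.
- Section 6.1: "Subjects will also be given a 9-week course of oral corticosteroid starting 3 days before surgery".

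Two places limit it:

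- Section 6.3: "subjects receiving AAV8-RPGR will be given a course of oral corticosteroid".
- The footnote to the steroid-dispensing row of Table 3 (Section 16.1): "Part II subjects in treated groups will be given a 9-week course of oral prednisone/prednisolone".

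A further Table 3 footnote restricts monitoring of the course: "Corticosteroid review is applicable only for treated subjects".

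**The concern.** Part II has a randomised untreated arm that is the comparator for both safety and efficacy, and Part II enrols from age 10. Randomisation and steroid dispensing both sit at Visit 1, so a site knows the subject's arm (though not the dose) when it decides whether to dispense. A site that follows Sections 8.8 and 9.1 would dispense to a control. A site that follows Section 6.3 or the Table 3 footnote would not. If sites differed, steroid exposure in the control arm would vary, and the adverse-event comparison would be made against an arm that is not uniformly untreated.

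Such a control would also fall outside the corticosteroid compliance review. Section 8.8 asks for attention to steroid side effects during the course, but controls have telephone calls only at Visits 2, 3 and 4, so their first on-site visit after screening is Month 1.

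**Working it through.** The plan states no figure on this point. The check compares the passages and then sizes the course.

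**Recipients and timing, place by place**

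| Place in protocol | Recipients as written | Start counted from |
|---|---|---|
| Section 8.8 | all Part II subjects | surgery |
| Section 9.1 | subjects, no arm named | Visit 2 |
| Synopsis | all adults in Part II | surgery |
| Section 6.1 | subjects, no arm named | surgery |
| Section 6.3 | those receiving the vector | not stated; refers to 8.8 |
| Table 3 footnote | treated groups only | Visit 2; refers to 8.8 |

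**Does the timing settle it?** For the Section 8.8 regimens, the synopsis and Section 6.1 it helps, because a control has no surgery date from which to count. For Section 9.1 it does not. Controls have a Visit 2, by telephone (Section 9.2 and a Table 3 footnote), so a start 3 days before it can be carried out in the control arm.

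**Does the surrounding text in Section 9.1 settle it?** No. The instruction follows shortly after the paragraph in which Part II subjects are told whether they are in a treatment group or the control group. The next instruction, on contraception, is qualified as applying only where relevant. The steroid instruction carries no such qualifier.

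**Do the cross-references settle it?** No. Section 6.3 and the Table 3 footnote both send the reader to Section 8.8 for the regimen, and Section 8.8 is where the unrestricted statement stands.

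**Size of the course, from the Section 8.8 schedules**

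- Duration: Day -3 to Day 17 is 21 days, plus 6 taper steps of 7 days: 21 + 42 = 63 days, which agrees with the stated 9 weeks.
- Adult total: 21 × 60 + 7 × (50 + 40 + 30 + 20 + 10 + 5) = 1,260 + 7 × 155 = 1,260 + 1,085 = 2,345 mg.
- Pediatric total, as a multiple of the weight-based starting dose: 21 + 7 × (0.83 + 0.67 + 0.5 + 0.33 + 0.17 + 0.08) = 21 + 7 × 2.58 = 39.06 times that dose.

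**Subjects concerned.** About 30 subjects allocated 1:1:1 gives about 10 controls. The power statement in Section 12.1 uses 9.

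**Would control use be seen?** Section 8.8 requires prednisone/prednisolone to be recorded among concomitant medications in the eCRF. Concomitant medication is reviewed with controls at the Visit 2, 3 and 4 calls and at every later visit. SAP Section 7.10 tabulates non-ocular concomitant medication by treatment group in the Safety Analysis Set, which includes controls who had the Visit 2 call. It also provides a listing of oral corticosteroid treatment and tapering.

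**The case against.** The strongest reply is that the loose wording misleads nobody. Section 8.8 gives the purpose of the course as limiting inflammation from surgery and from the vector or transgene, and neither applies to a control. The protocol uses unrestricted wording elsewhere for steps that controls plainly do not undergo, such as vitrectomy in Section 6.1. The Table 3 footnote gives nearly the same instruction as Section 9.1, also timed from Visit 2, with the restriction added, and Section 9 opens by pointing to Table 3. Section 8.6 treats notes of peri-operative corticosteroid as a possible source of unmasking, which suggests that use was expected to differ between arms.

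Much of this stands, and it lowers the practical risk: many sites would probably not have dispensed to controls. It does not remove the conflict. Section 8.8 makes its statement about all Part II subjects, and Section 9.1 lacks the surgery anchor on which the contextual reading depends.

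It is also fair to reply that rewording now has little prospective effect. The Version 11 amendment summary gives 30 September 2019 as the close of enrolment, and Version 11 is dated 1 October 2020. That stands too, and it makes the check of recorded medication the more useful half of the remedy.

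A reader might infer that steroid use by a control would go unseen. The documents do not support that. Only the compliance review is limited to treated subjects, and concomitant-medication recording covers everyone.

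**Conclusion.** The point holds as a contradiction within the current protocol about who receives the Part II oral steroid course. Section 8.8 and Section 9.1 are the passages that matter most. The synopsis and Section 6.1 are also unrestricted in wording, but they are timed from surgery. On the literal reading, the exposure is 63 days for about 10 of about 30 subjects, 2,345 mg for an adult and weight-based for a child, without the compliance review. That size assumes equal allocation and the full course as written.

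Two further inferences are tempting and not supported. One is that controls were actually given the course; nothing in the documents shows this. The other is that the Month 12 primary comparison is compromised. The written course ends on Day 59, and no passage says that steroids affect microperimetry at Month 12, so no claim is made about efficacy. Nor is any view taken on which recipient group is correct; the passages have to be reconciled by those responsible for the protocol.

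**What to change.** Reconcile Sections 8.8, 9.1 and 6.1 and the synopsis with Section 6.3 and the Table 3 footnote so that every place names the same recipients of the Part II course. This is a change of protocol wording only.

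Because rewording cannot alter dispensing that has already happened, also check the non-ocular concomitant-medication tables and the oral corticosteroid listing planned in SAP Section 7.10 for any control who took the course, and flag any such subject in the safety outputs. The tables and listing are already planned and the data already collected, so the added cost is one check and, if needed, a flag with a footnote. If no control took the course, one sentence in the study report saying so closes the matter.
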